8.4 Reporting SAEs

SAEs will be collected for all patients until discharge from hospital.

SAE reporting for non-CTIMPS must be made to the sponsor within 1 working days of the research team becoming aware of the SAE and following a clinical review by the chief investigator. The SAE also must be reported to the main research ethics committee (REC) on the health research authority (HRA) approved non CTIMP SAE report form by the research team within 15 days of the CI becoming aware of the event. The sponsor will also be informed of the event on [contact].

Identifiable patient data, other than linked anonymised data required by the SAE form will not be included when reporting SAEs.

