2.3 Rationale for the proposed study

It is hypothesised that the SensiumVitals[®] system, as an adjunct to standard NEWS monitoring, will allow earlier detection of postoperative complications. This should reduce morbidity, which in turn should result in a decreased need for high dependency/intensive care.

3. Study objectives

To evaluate the safety, efficacy and acceptability of a new, wearable, remote monitoring system (SensiumVitals[®]) for patients admitted to surgical wards, as compared to standard monitoring with the National Early Warning Score system alone.

4. Study design

This is a single-centre feasibility study. Patients will be selected on the basis they are admitted to one of four general surgery wards. We will include 500 patients, most of whom will undergo a surgical procedure during their hospital stay.

When patients are admitted to a general surgery ward, they are allocated a bed by a team of 'bed managers' based on clinical need and availability. Each of the participating general surgery wards is divided into 'bays' of four or six beds, and 'side rooms' which contain only one bed. Prior to the commencement of the study, each bay and side room on each of the participating wards will be randomly allocated to receive 'patched' patients, or NEWS-monitored controls. The randomisation of bays will be balanced for ward type, taking account of patient gender and surgical subspecialty.

Patients will be identified as potentially eligible to participate in the study and approached on admission to the surgical wards. At this point they will be given further information in the form of a patient information sheet regarding the study. Following a period of consideration, if they have decided to participate in the study they will receive the appropriate monitoring. Information will also be collected regarding the number of patients who agree to take part in the study, those who do not and the reason for not taking part.

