For the duration of the study, when a patient is admitted to one of the participating wards, they will be allocated to one of the two study arms according to the bay or side room to which they are allocated by the bed managers. The bed managers are removed from ward-based care and the allocation of a patient to a particular bed is 'random' and avoids selection bias. Eligible patients in the 'patch' bays/side rooms will receive a patch and standard NEWS monitoring. Patients in the 'control' bays/side rooms will receive standard NEWS monitoring alone.

All usual nursing and medical care are permitted within both arms of the trial. This includes fluid balance monitoring, neurological observations, etc.

Roughly half of the patients (250) will be offered the new system. The devices are designed to be lightweight and unobtrusive, with a battery life of 5 days. Patients will be expected to wear the device for the duration of their hospital admission. The device will monitor the patient's heart rate, respiratory rate and temperature continuously, and send this information every two minutes to a mobile device carried by the patient's nurse. The information is also available on the ward computer monitors.

The patients will remain in their allocated study arm for the duration of their hospital stay. If a 'patched' patient is moved to a critical care bed during their admission, the SensiumVitals[®] monitoring will be temporarily suspended pending reinstatement depending on the ward bed to which they return. Every effort will be made to ensure that patients remain in the study arm to which they were originally allocated, and any non-compliance will be recorded. Analysis will be on an intention-to-treat basis.

Patients' participation in the trial will end when they are discharged from hospital. At this point, 'patched' patients will be invited to complete a questionnaire and /or undertake a structured interview regarding their experiences of wearing the patch. Patients will also be invited to attend one or more focus groups after discharge from hospital. Information regarding the admission will be collected once the patient has left hospital.

The staff nurses will be invited to complete a paper questionnaire in the form of a Modified System Usability Score. They will also be invited to undertake a structured interview regarding their experience of providing the new monitoring system.

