8.2 Defining serious adverse events (SAEs)

A SAE is defined in general as an untoward (unfavourable) event, which:

• is fatal. Death may occur as a result of the basic disease process. Nevertheless, all deaths occurring within 30 days of the last administration of the study agent must be treated as an SAE and reported as such. All deaths which may be considered as related to the trial agent, regardless of the interval, must be treated as a SAE and reported as such.

- is life-threatening
- requires or prolongs hospitalization
- results in persistent or significant disability or incapacity
- is a congenital anomaly or a birth defect, or
- may jeopardise the patient and may require medical or surgical intervention to prevent one of the outcomes listed above

Any other significant clinical event, not falling into any of the criteria above, but which in the opinion of the investigator requires reporting.

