8.3 Reporting AEs

AEs will be collected for all patients and will be evaluated for duration and intensity according to the NCRI Common Toxicity Criteria.

Safety will be assessed by review of adverse events from the time of registration into trial to 30 days post-operatively.

Information about AEs, whether volunteered by the patient, discovered by the investigator questioning or detected through physical examination, laboratory test or other investigation will be collected and recorded.

A copy of all reported AEs will be sent to the sponsor if requested.

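### Sections 8.2, 8.3 and 8.4 give conflicting ends to safety follow-up: two have no date for some patients, and the SAE cut-off moves with length of stay

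*Protocol*

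**What the plan says.** The protocol sets the end of safety follow-up in five places.

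- **Section 8.4:** "SAEs will be collected for all patients until discharge from hospital".
- **Section 8.3:** AEs are collected for all patients, and safety is assessed by "review of adverse events from the time of registration into trial to 30 days post-operatively".
- **Section 8.2:** "all deaths occurring within 30 days of the last administration of the study agent must be treated as an SAE and reported as such". Deaths thought to be related to the agent are reportable whatever the interval. An event is also serious if it "requires or prolongs hospitalization", which takes in readmission.
- **Section 4:** patients' "participation in the trial will end when they are discharged from hospital".
- **Section 5.2.6:** the trial ends on the discharge date of the last recruited patient.

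Other text bears on how these apply. Controls have NEWS monitoring only (section 4). The 500 patients are a group "most of whom will undergo a surgical procedure during their hospital stay", so some will have no operation. Total length of stay is a secondary outcome (section 4.1.2). Complications and re-interventions are listed in the same section without a time window. Safety relative to standard monitoring is part of the objective (section 3). The arms are to be summarised descriptively, with no formal comparison (section 5.1.3).

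**The concern.** SAEs are a subset of AEs, so the two should not have different closing dates unless the plan says why. Here they do, and the death clause adds a third date. Site staff cannot tell whether an event in the weeks after discharge has to be looked for, recorded or reported. The protocol describes no contact or record check after discharge that would bring such events to light.

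Two of the three limits also start from something that not every patient has: a study agent, or an operation. The third, discharge, is defined for everyone but is not neutral. If monitoring changes how long patients stay, it changes how long they are observed for SAEs.

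At stake are the completeness of serious event reporting, the fairness of the by-arm safety summaries, and the safeguard in section 11.1. That safeguard relies on recognising complications in excess of what is usual, which needs a defined period of observation.

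**Working it through.** The protocol gives no calculation on this point, so there is no figure to reproduce. The check is mainly a comparison of dates.

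**Step 1: closing dates by type of patient.** Day 0 is surgery for operated patients and registration for the others. The patch is taken as worn to discharge, as section 4 expects, and the last day of wear is read as the last 'administration'. For discharge on day L, SAE collection ends on day L, AE review on day 30 and the death clause on day L + 30.

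| Patient | SAE (8.4) | AE (8.3) | Death clause (8.2) |
|---|---|---|---|
| Operated, patch, L = 7 | 7 | 30 | 7 + 30 = 37 |
| Operated, patch, L = 35 | 35 | 30 | 35 + 30 = 65 |
| Operated, control, L = 7 | 7 | 30 | no date |
| Not operated, patch, L = 7 | 7 | no date | 37 |
| Not operated, control, L = 7 | 7 | no date | no date |

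For an operated patient with a patch the three dates never coincide, because the first and third are always 30 days apart. With discharge before day 30 the serious events have the shorter window. With discharge on day 35 the order of the AE and SAE limits reverses.

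**Step 2: one event, three answers.** Take discharge on day 7 after surgery and an event on day 20.

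- *Death, patch arm:* inside 8.3 (20 ≤ 30) and inside 8.2 (20 ≤ 37), outside 8.4 (20 > 7).
- *Death, control arm:* inside 8.3, outside 8.4. The 30-day clause in 8.2 has no date to count from. The death is still serious by definition, since 8.2 lists fatal events without regard to arm.
- *Readmission, either arm:* serious under 8.2, inside 8.3, outside 8.4.

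Under sections 4 and 5.2.6 participation has already ended in every one of these cases.

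**Step 3: direction of the effect of a discharge cut-off.** The inputs here are assumptions, because the protocol gives no length of stay and no SAE rate. Let both arms have the same constant event hazard, so that the true ratio is 1. With 30-day risk p, λ = −ln(1 − p)/30, and the fraction of patients with an event before discharge on day L is 1 − exp(−λL). Take 250 per arm, from section 4.

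For p = 0.30, λ = 0.3567/30 = 0.01189.

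- Control, L = 7: 250 × (1 − exp(−0.0832)) = 20.0 events.
- Patch, L = 5: 250 × (1 − exp(−0.0594)) = 14.4 events.
- Apparent ratio: 14.4/20.0 = 0.72.
- Fixed 30 days: 250 × 0.30 = 75 events in each arm, ratio 1.00. The discharge cut-off sees 20.0/75 = 27% and 14.4/75 = 19% of these.

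| Assumed stay, control vs patch (days) | Apparent ratio, p from 0.10 to 0.40 |
|---|---|
| 5 vs 4 | 0.80 to 0.81 |
| 7 vs 6 | 0.86 |
| 7 vs 5 | 0.72 to 0.73 |
| 10 vs 8 | 0.80 to 0.81 |
| 14 vs 10 | 0.72 to 0.74 |

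The ratio is close to the ratio of the assumed stays and hardly depends on p. With equal stays it is 1.00. The table shows direction and mechanism and does not estimate what will happen in this study.

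**The case against.** The best case on the other side accepts that the sections conflict and disputes how much follows. Five stronger readings are tempting, and the document does not support them.

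- *The windows cannot be applied to controls or to non-operated patients at all.* Section 8.4 covers all patients, and section 8.3 covers operated controls. Only the agent clause fails for controls, and only the post-operative date fails for patients without surgery.
- *Deaths after discharge would be counted in the patch arm alone.* Section 8.3 takes AEs from all patients, so a death within 30 days of surgery is in scope in both arms. What differs by arm is the explicit 30-day reporting duty in 8.2. The lack of a described route to find such deaths affects both arms.
- *Complications and re-interventions also stop at discharge.* No window is stated for them. That they stop there is only an inference from section 4, which says that information on the admission is collected once the patient has left. Their windows may be set in a statistical analysis plan.
- *The distortion can be put as a percentage.* It rests on assumed stays and risks. The 30% to 40% complication rate in section 2.1 has no time frame and refers to major abdominal procedures, whereas section 5.1.1 admits all patients on the wards. The illustration also treats stay as fixed and unaffected by events, although 8.2 counts prolonged hospitalisation as serious, so stay depends partly on the events themselves.
- *A treatment comparison is invalidated.* Section 5.1.3 plans none, and the primary outcome in section 4.1.1 does not use these windows.

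All of this limits the size and reach of the point. It leaves the contradiction among 8.2, 8.3 and 8.4 and the missing start dates in place. An analysis plan could not repair them, because they govern what is collected and reported.

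**Conclusion.** The point holds as a contradiction in the safety rules and needs no assumed figures for that. Sections 8.2, 8.3 and 8.4 cannot all be followed for a patient with a serious event after discharge but within 30 days of surgery, and sections 4 and 5.2.6 close follow-up at discharge. The agent clause is undefined for controls and the post-operative limit is undefined for non-operated patients, whose number the protocol does not give.

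The discharge cut-off for SAEs can also make the arm with the shorter stay look safer in a descriptive summary. This requires that stay differs between arms and that some events fall after discharge. Its size cannot be stated from the protocol.

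The consequence is incomplete or uneven serious event reporting and by-arm safety summaries that are hard to interpret, in a study with safety among its objectives. With descriptive analysis only and the primary outcome unaffected, this should be fixed but does not undermine the study as a whole.

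**What to change.** Reconcile sections 4, 5.2.6, 8.2, 8.3 and 8.4 as follows.

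1. Define one safety window for AEs, SAEs and deaths, starting from a time zero that every patient in both arms has, for example registration.
2. Replace the 'study agent' wording in 8.2 with dates counted from that time zero.
3. Summarise safety, complications and re-interventions by arm over a fixed 30 days from time zero, using hospital records.
4. Continue collecting and reporting beyond those 30 days until discharge or 30 days post-operatively, whichever is later. A window that simply closed 30 days after registration would lose later in-hospital SAEs, and part of the post-operative period for anyone operated on after registration.
5. State explicitly what happens to deaths between that point and 30 days after the patch is removed, which 8.2 now covers for patched patients only. Whatever is decided should apply to both arms.
6. Move the end of participation and the end of trial so that they do not precede this follow-up.

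The cost is protocol wording, matching consent text and a 30-day record check for each patient. Some events treated at other hospitals may be missed, and it should not be assumed that they are missed equally in the two arms.

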8.5 Pregnancy

Pregnancy will not be a contra-indication to study participation.

8.6 Annual reports

An annual report describing the general progress and any relevant safety data related to the trial must be submitted to the main REC and the sponsor.

8.7 End of trial report

Upon completing the trial, as defined in 5.2.6, an end of trial report must be submitted to the main REC within 90 days. A copy of this end of trial report should also be submitted to the sponsors office and supplied to all support departments involved in the study, for example pharmacy and or radiology.

The CI must sign and date the report.

9. Data management

9.0 Data collection, source data and confidentiality

The SJUH site will maintain a file of essential trial documentation (Investigator Site File, ISF) and will keep copies of completed CRFs for the trial, or a file note to their location, as well as copy of the patient enrolment and allocation log within the ISF.

Data will be collected using paper case report forms (CRFs). CRFs will only be completed by personnel authorised to do so by the Principal Investigator.

All information collected during the course of the trial will be kept strictly confidential.

Information will be held securely on paper and electronically at Leeds Teaching Hospitals NHS Trust.

The trial group will comply with all aspects of the Data Protection Act 1998 and operationally this will include:

• consent from patients to record personal details including name, date of birth, address and telephone number, NHS ID, hospital ID, GP name and address

• appropriate storage, restricted access and disposal arrangements for patient personal and clinical details

• consent from patients for access to their medical records by responsible individuals from the research staff, the sponsor or from regulatory authorities, where it is relevant to trial participation

• consent from patients for the data collected for the trial to be used to evaluate safety and develop new research

9.2 Data archiving

In line with the principles of GCP guidelines, at the end of the trial, data will be securely archived for a minimum of 5 years. This data will include that collected in the clinical reporting forms and will also include recordings.

Arrangements for confidential destruction will then be made. If a patient withdraws consent for their data to be used, it will be confidentially destroyed immediately. No records may be destroyed without first obtaining written permission from the sponsor.

Study documentation / data will not be destroyed without the approval of the sponsor.

10. Statistical considerations

10.1 Sample size

This is a single centre feasibility study, and as such no formal sample size calculation has been made.

11. Data monitoring

11.1 Data monitoring

As this is a feasibility study, data will be monitored prospectively by the research team. Any clinical concerns, or complications occurring in excess of those normally experienced in this type of surgery, will be reported by the PI to the sponsors and appropriate action taken to suspend or terminate the study until such time that patient safety can be assured in line with national guidelines for patient outcomes in surgery.

11.2 Quality assurance

The Sponsor has systems in place to ensure that there is reporting and appropriate action taken in respect of:

• Serious breaches of GCP and the trial protocol

- Urgent safety Measures
- Protocol violations

A "serious breach" is a breach which is likely to effect to a significant degree:

- The safety or physical or mental integrity of the subjects of the trial; or
- The scientific value of the trial".

Investigators will promptly notify the Sponsor of the following within the required timeframe, once they become aware of:

- Serious breaches of GCP and the trial protocol
- Urgent safety Measures
- Protocol violations
- Any amendments to the trial

12. Ethical considerations

The trial will be performed in accordance with the recommendations guiding ethical research involving human subjects adopted by the 18th World Medical Assembly, Helsinki, Finland, 1964, amended at the 48th General Assembly, Somerset West Republic of South Africa, October 1996. Informed written consent will be obtained from the patients prior to registration into the study. The right of a patient to refuse participation without giving reasons will be respected. The patient will remain free to withdraw at any time from the study without giving reasons and without prejudicing his/her further treatment. The study will be submitted to and approved by a REC.

13. Statement of indemnity

Clinical negligence indemnification will rest with the participating NHS Trust or Trusts under standard NHS arrangements. The Trust does not provide indemnification against claims arising from non-negligent harm.

14. Publication policy

Credit for the main results will be given to all those who have collaborated in the study, through authorship and contributorship. Authorship decisions will be guided by standard requirements for authorship relating to submission of manuscripts to medical journals. These state that authorship credit should be based only on the following conditions being met:

• Substantial contribution to conception and design, or acquisition of data, or analysis and interpretation of data

• Substantial contribution to drafting the article or revising it critically for important intellectual content

• Substantial contribution to final approval of the version to be published.

15. Appendices

- 1) Patient questionnaire
- 2) Modified system usability score

- 3) Topic guide for interviews with nursing staff
- 4) Topic guide for interviews with patients

learn to use this product very quickly	1	2	3	4	5
I found the product very awkward to					
use	1	2	3	4	5
I folt you confident using the product					
Their very confident using the product					
	1	2	3	4	5
I needed to learn a lot of things					
before I could get going with this					
product	1	2	3	4	5

3) Topic guide for interviews with nursing staff

Documentation of demographic details (anonymised)

Introduction

- Thanks for helping
- Introduce the aim of the interview
- Emphasise confidentiality and anonymisation
- There are no right or wrong answers: "This is simply about your experience of the way we monitor patients on this ward."
- Introduce dictaphone
- Invite questions

Questions

Over the last few months you've been involved in the study of the SensiumVitals® monitoring system, patching patients in your care.

How did you feel when you were told you would be using the new monitoring system?

- What was your experience of using the patch system?
- Were there good things about the system? If yes, what were they?
- Were there bad things about the system? If yes, what were they?

Additional prompts, if needed:

- Did the patients like it?
- Did it cause you any bother?
- Did you like it? Why/Why not?
- Did you feel the patients were safer wearing it?
- Would you have changed anything about it?
- Would you use it again?
- Would you recommend it to other wards? If yes, what would you say?
- What suggestions would you make to improve the system?
- How could the system be made to be more appealing to nurses like you?

Whilst studying the SensiumVitals[®] system, you still administered regular NEWS rounds to all of your patients.

- What is your experience of these observation rounds?
- Are there good things about them? If yes, what are they?
- Are there bad things about them? If yes, what are they?
- How would you feel if you didn't do NEWS rounds, and just used the SensiumVitals[®] system?
- How do you think we can improve the way we monitor patients in hospital?

Conclusion

- Signpost the end of the interview
- Invite further questions
- Thanks for taking part
- Ask if the nurse would like to be kept informed about the study

4) Topic guide for interviews with patients

Documentation of demographic details (anonymised)

Introduction

- Thanks for helping
- Introduce the aim of the interview
- Emphasise confidentiality and anonymisation
- There are no right or wrong answers: "This is simply about your experience of the way you were monitored during your stay in hospital."
- Introduce dictaphone
- Invite questions

Questions

During your hospital stay, you wore a patch on your chest which helped the nurses monitor your progress.

How did you feel when you were told that you had been put into the group wearing the patch?

- What was your experience of wearing the patch?
- Were there good things about wearing the patch? If yes, what were they?
- Were there bad things about wearing the patch? If yes, what were they?

Additional prompts, if needed:

- Was it comfortable?
- Did it bother you in any way?
- Did you like it? Why/Why not?
- Did you feel safer wearing it?
- Would you have changed anything about it?
- Would you have it again?
- Would you recommend this intervention to other patients? If yes, what would you say?
- What suggestions would you make to improve the patches?
- How could the patches be more appealing to patients like you?

During your hospital stay, you will also have been monitored by one of the nursing staff, coming round every few hours to check your blood pressure, etc. with a machine.

- What was your experience of these observation rounds?
- Were there good things about them? If yes, what were they?
- Were there bad things about them? If yes, what were they?
- How would you feel if you were just monitored in this way, without the patch?
- How would you feel if you just had the patch?

Additional prompts, if needed:

- Did it bother you in any way?
- Did you like it? Why/Why not?
- Did it make you feel safer?
- Would you have changed anything?

"The two monitoring techniques (patch vs. nurse with machine) help to keep an eye on your progress, and let the nurses know if anything is going awry."

• What do you think about the way we monitor patients in hospital?

Conclusion

- Signpost the end of the interview
- Invite further questions
- Thanks for taking part
- Ask if the patient would like to be kept informed about the study
- Invite to focus groups

5) Topic guide for focus group 1:

Documentation of attendees (anonymised)

Introduction

- Thanks for helping
- Housekeeping (fire exits, etc.)
- Introduce the facilitators
- Introduce the aim of the focus group and time schedule
- Emphasise confidentiality and anonymisation
- There are no right or wrong answers: "This is simply about your experience of the way you were monitored during your stay in hospital."
- Introduce dictaphone
- Invite questions

Questions

During your hospital stay, you wore a patch on your chest that helped the nurses monitor your progress.

How did you feel when you were told that you had been put into the group wearing the patch?

What was your experience of wearing the patch?

- Were there good things about wearing the patch? If yes, what were they?
- Were there bad things about wearing the patch? If yes, what were they?

Would you have changed anything about it?

What was your experience of being in the study?

- Did you enjoy being in the study? Why?
- Were there things you didn't like about being involved in the study? What were they?

How would you change the study to make it better for other patients taking part?

Conclusion

• Signpost the end of the focus group

- Invite further questions
- Thanks for taking part
- Explain how information will be used

6) Topic guide for focus group 2:

Documentation of attendees (anonymised)

Introduction

- Thanks for helping
- Housekeeping (fire exits, etc.)
- Introduce the facilitators
- Introduce the aims of the focus group and time schedule
- Emphasise confidentiality and anonymisation
- There are no right or wrong answers.
- Reintroduce dictaphone
- Invite questions

Questions

Since we last met, is there anything you wanted to add regarding your experience of the patch, or the study itself?

Brief summary of results so far, including patient interviews. Outline of plans for dissemination.

Questions

You were sent a summary of the study via email. It is intended to be read and understood by members of the public.

- Did you understand it?
- How could it be made more clear?

How would you like to see the results of the study used? Who needs to know about this?

Conclusion

- Signpost the end of the focus group
- Invite further questions
- Thanks for taking part
- Explain how information will be used

Figures

1) SensiumVitals[®] patch

2) SensiumVitals monitoring system: wireless transfer of patient's vital signs to mobile device
